Informed by the modeling of secular trends, the final models will add in indicator terms for whether the observation occurred before or after the intervention, in addition to the appropriate modeling of secular trends. Additional more sophisticated modeling will evaluate the trends in the outcomes over time in the post-intervention periods to see whether temporal trends differ pre-and post- intervention. All statistical tests will be two-sided and will be considered to be significant if the associated p-value is <0.05. All analyses will be intention-to-treat based on the unit’s assignment at the time of a patient’s admission, and missing data will be imputed using a multiple imputation strategy, based on the characteristics of the data.

AIM 1: To test the effectiveness of a mobility program on recovery to pre-hospital mobility status or better and reduction of adverse outcomes in the year after hospitalization.

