To test the effectiveness of the intervention on mobility, LSA scores and changes in LSA scores for patients in the control condition will be compared to LSA scores from patients in the intervention condition. Mixed models will be used to examine and compare mean LSA over time with time considered a random effect. An indicator term will be included to denote whether the observation was from the period prior to or after implementation of the intervention. The indicator term will represent whether there was an overall difference in the LSA during the intervention period versus the pre-intervention period, and its statistical significance in the model for each outcome will be the primary test of whether the intervention had a significant effect on LSA. A priori we believe that an exchangeable covariance structure will be most suitable for the data. For the secondary hypotheses, i.e., self-reported outcomes for driving (yes/no) and ability to walk $\frac{1}{4}$ of a mile (yes/no), generalized linear mixed models (GLMMs) that account for repeated measures will be used to compare pre- and post-intervention periods. Given the randomized nature of the study design, adjustment for potential confounders will likely be unnecessary as they are expected to be equally distributed between the groups. However, as noted above, we will confirm that any potential confounders, e.g., age, length of hospitalization, and disease burden score (Cumulative Illness Rating Scale-Geriatrics, or CIRS-G²³) are indeed similar between the pre- and post-intervention periods and, should any not be, we will adjust for them in the statistical models provided they are not deemed to be consequences of the intervention.

To test the effectiveness of the intervention on adverse outcomes, we will use mixed models and GLMMs to model changes in functional decline (ADLs and IADLs), number of ED visits, and number of hospitalizations with an approach similar to the above. To test the effectiveness of the intervention on nursing home admission

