and death, we will use Cox proportional hazards models to compare the time from hospital discharge to the time to event between the MP and UC groups, adjusting for potential covariates. Due to the potential interrelationship between risk of nursing home admission and risk of death, competing hazards will be used to model the time to occurrence of the first event. Right censoring of participants will occur with dropout due to any reason (death, loss to follow-up, conclusion of the study period, etc.). Multiple imputation techniques will be used to offset potential bias due to missing predictors in the models.

AIM 2: To identify characteristics which modify the effect of the mobility intervention on recovery to pre-hospital mobility status or better and reduction of adverse outcomes in the year after hospitalization.

Potential effect modifiers include pre-admission ADL and LSA, cognitive function, level of in-hospital mobility, depressive symptoms, and social support. For continuous variables, e.g., activities of daily living score, overall distributions will be reviewed and categorized as low, medium and high based on tertile cut-points. To test for significant effect modification, single second level interaction terms, combining pre-/post-intervention indicators with potential effect modifiers, will be added to mixed models. Resulting F-tests for the interaction terms will be reviewed and p-values <0.05 identified as significant. Examination of potential effect modifiers based upon their tertile groupings not only allows for the identification of significant factors but also has the added benefit of examining factor's dose effect, providing additional internal validity to the analysis.

F. ECONOMIC CONSIDERATIONS: *Describe any material inducements that will be offered to subjects in return for their participation: e.g., direct payment, free services, etc. Describe any schedule of payment to subjects based on their complete or partial participation. Will early withdrawal from the study result in a reduced payment? Does it make a difference whether it is the subject or the investigator who decides to terminate the subject's participation? Explain any bonus a subject may receive for completion of the study. These partial or bonus payments must also be explained in the consent form.*

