Implementation/Dissemination: This research holds great promise as we begin to define a standard of care for hospital mobility, which is currently lacking. With the success of this proposal we will have demonstrated the effectiveness of this program on mobility and adverse outcomes after hospitalization as well as identified patient characteristics that modify the intervention effects. It is critical to develop a robust evidence base for mobility during hospitalization as hospitals all across the country and the world are currently grappling with the issue of low mobility and its consequences. As noted by a recent review by Kalisch, "Interventions and policies that increase inpatient mobilization need to be developed, tested and put into practice."⁶ This study would provide the type of data needed to develop VA policies and a standard of care for safe mobility for all hospitalized veterans. Future steps would include a multicenter trial to assess the generalizability of the program followed by dissemination of the mobility program to VA hospitals across the nation.

We propose a multi-level dissemination plan designed to target research findings to several different audiences. First, we will use traditional dissemination through the publication of high-quality peer-reviewed articles throughout the study's conduct, including empirical, methodological, and theoretical manuscripts. Manuscripts summarizing results will be targeted to (1) management-oriented journals (e.g., Journal of Nursing Management); (2) clinical nursing, physician and physical therapy journals (e.g., Journal of Hospital Medicine); and quality improvement and implementation oriented journals (e.g., Journal of Nursing Care Quality, Implementation Science). We will deliver presentations to research and policy-oriented audiences. It is imperative also that we bring early results to VA-specific audiences including VISN, facility, and nursing leadership; nurse managers, rehabilitation managers and frontline staff. We will use written, oral and web-based dissemination strategies to bring early results to these stakeholders. Examples include reporting through relevant approved Central Office publications (e.g., newsletters, web-based material), as well as reporting to groups of stakeholders who

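### Aim 2 calls any interaction with p<0.05 significant across at least six modifiers and several outcomes, with no multiplicity control and no exploratory label

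*Protocol*

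**What the plan says.** The third purpose in protocol section A is to find out which patients benefit most. Aim 2 (protocol section E, Analytic Approach) turns this into a specific aim: "To identify characteristics which modify the effect of the mobility intervention on recovery to pre-hospital mobility status or better and reduction of adverse outcomes". The candidates are given as follows: "Potential effect modifiers include pre-admission ADL and LSA, cognitive function, level of in-hospital mobility, depressive symptoms, and social support". That is six, and the word 'include' leaves the list open.

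The method is one modifier at a time: "single second level interaction terms, combining pre-/post-intervention indicators with potential effect modifiers, will be added to mixed models". Continuous modifiers are cut into tertiles. The decision rule is "Resulting F-tests for the interaction terms will be reviewed and p-values <0.05 identified as significant". It agrees with the general rule earlier in the same section: "All statistical tests will be two-sided and will be considered to be significant if the associated p-value is <0.05". The SAP's Aim 2 section repeats the method and the rule.

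The SAP's Implementation/Dissemination section says that, if the proposal succeeds, the study will have "identified patient characteristics that modify the intervention effects".

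Neither document contains a multiplicity adjustment, a primary modifier, a primary Aim 2 outcome, or a statement that the interaction analyses are exploratory.

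**The concern.** A rule that labels each p-value below 0.05 significant controls error one test at a time. Aim 2 asks a different question, namely which of a list of characteristics modifies the effect, and it asks it for more than one outcome. The chance that at least one characteristic is named wrongly therefore grows with the number of tests, and nothing in the plan limits it.

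What is at stake is the answer to the third stated purpose. A chance interaction on, say, depressive symptoms could be reported as a finding about who benefits. The plan encourages that reading: it says that the tertile analysis identifies significant factors and adds internal validity, and the SAP counts identified modifiers among the study's results. The Aim 1 test of the overall LSA effect is not affected.

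**Working it through.** The documents give no error rate, false-positive count or power for Aim 2, so there is no figure of the plan's own to reproduce. All figures below assume no true effect modification.

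**Inputs from the documents**
- Threshold: 0.05 per interaction F-test (Aim 2, both documents).
- Modifiers: six named, taken as a minimum.
- Outcomes: Aim 2 lists none, so they are read from Aim 1. Mobility is LSA plus two self-reports: "For the secondary hypotheses, i.e., self-reported outcomes for driving (yes/no) and ability to walk" a quarter mile. Adverse outcomes analysed by mixed models or GLMMs are four: "model changes in functional decline (ADLs and IADLs), number of ED visits, and number of hospitalizations with an approach similar to the above". That makes seven. Nursing home admission and death are analysed by Cox models and are not counted here.

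**Formulas**
- Expected false modifiers = k × 0.05 for k tests, whatever the correlation between them.
- Chance of at least one = 1 − 0.95^k if the tests are independent.

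**Results**

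| Outcomes tested | k | Expected | At least one (independent) | At least one (assumed correlations) |
|---|---|---|---|---|
| LSA only | 6 × 1 = 6 | 0.3 | 1 − 0.95^6 = 26% | 21-27% |
| LSA, ADL, IADL | 6 × 3 = 18 | 0.9 | 1 − 0.95^18 = 60% | not simulated |
| All seven mixed-model/GLMM outcomes | 6 × 7 = 42 | 2.1 | 1 − 0.95^42 = 88% | 60-88% |

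The 18-test row assumes that Aim 2's reference to mixed models means only the outcomes modelled as continuous, taken here to be LSA, ADL and IADL.

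The last column comes from simulation of two-degree-of-freedom tests (tertiles), 40,000 runs per scenario. The documents give no correlations. The assumed range is 0 to 0.5 among modifiers and 0 to 0.7 among outcomes. For LSA, the chance is 21% at a correlation of 0.5 among modifiers. The upper end of 27% is the simulated value at independence, where the exact figure is 26.5%. For 42 tests, correlations of 0.5 and 0.7 give 60%, 0.3 and 0.5 give 76%, and independence gives 88%.

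**Power cost of an adjusted confirmatory test on LSA.** The plan claims more than 90% power for a 10-point LSA difference. Assume exactly 90%: the standard error is 10 / (1.960 + 1.282) = 3.08. With equal tertiles, each tertile effect has a standard error of 3.08 × √3 = 5.34. For assumed true effects of 0, 10 and 20 points, the noncentrality is (10² + 0² + 10²) / 5.34² = 7.0. A two-degree-of-freedom test then has about 66% power at 0.05 and about 42% at 0.01.

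**The case against.** Testing named candidate modifiers by interaction is sound practice for a non-primary aim, and many readers would take such results as exploratory without being told. On LSA, the most likely result under no effect modification is no false modifier at all (0.95^6 = 74%). Adjustment also costs power, as shown above. These points stand. They argue for an exploratory label rather than for compulsory adjustment, but they do not supply the label, and the plan's own wording points the other way.

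Three stronger readings are tempting, and the documents do not support them.

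- *A false modifier is to be expected on every outcome.* The expected count on any one outcome is 0.3. It reaches 0.9 to 2.1 only when summed over outcomes.
- *All nine Aim 1 outcomes count, giving 54 tests, 2.7 expected and a 94% chance.* Aim 2 speaks of mixed models and F-tests, while nursing home admission and death are analysed by Cox models. These 12 tests may fall outside the rule, and 94% is in any case the ceiling under independence.
- *A false modifier would decide who is offered the program.* The SAP's dissemination section speaks of a standard of care for all hospitalized veterans, with a multicenter trial before wider roll-out. No section proposes limiting access to a subgroup.

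**Conclusion.** The point holds as a defect in a stated decision rule, not as missing detail. If the rule is followed exactly and there is no effect modification, the trial has about a one-in-four chance of naming a false modifier on its primary outcome. Across Aim 2's outcomes it would name between 0.9 and 2.1 on average.

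The expected counts depend only on the number of tests. The chances of at least one also depend on correlations that had to be assumed. The number of outcomes is read from Aim 1 and is uncertain because Aim 2 does not list them; six modifiers is a minimum. The harm is that a chance result may be presented as an established modifier. This deserves correction because the remedy costs almost nothing, but it does not threaten the primary analysis.

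**What to change.** In Aim 2 of both documents, replace the p<0.05 rule. Report every interaction as an estimate with a 95% confidence interval, label the analyses exploratory and hypothesis-generating, list the outcomes, and state how many interactions were tested. In the SAP's Implementation/Dissemination section, speak of candidate characteristics that may modify the intervention effects.

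If the sponsor wants a confirmatory claim, restrict it to LSA and to a closed list of five modifiers at their baseline values: pre-admission ADL, pre-admission LSA, cognitive function, depressive symptoms and social support. Apply Holm at 5% (first threshold 0.05 / 5 = 0.01). Level of in-hospital mobility should stay exploratory only, because it is measured after assignment and is what the program aims to raise. Protocol Table 3 allows the depression and social network measures to be completed at any time before discharge, so the report should say whether those values were taken before the first study visit.

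The cost is wording; no new data or patients are needed. The downside is that no single modifier can be declared significant on other outcomes. The optional Holm step also lowers interaction power, from about 66% to about 42% at the first threshold in the example above.

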Patients admitted to the medical wards of the BVAMC (4A, 4B, 5A, 5B, and 6B) and to medical wards at UAB Hospital (3 Hospitalist Units, and the Tinsley Harrison service) will be eligible to participate in this study. A brief screening interview will be conducted with the ward team to identify patients who meet eligibility criteria; if eligible, consent to interview the patient will be requested from the physician. Interviews to further determine eligibility and to obtain consent will be conducted in patient rooms. While a participant is hospitalized, study assessments, tests, and interventions will be conducted in patient rooms or, for walking sessions and gait speed assessments, in the hallways of the BVAMC or UAB Hospital. Post-discharge assessments will occur over telephone or, in the rare event that a patient has been re-hospitalized at BVAMC or UAB Hospital, in the participant's hospital room. Telephone assessments will be conducted from rooms 8211, 8223, 8224 and 8218 in the BVAMC. Study staff will conduct these assessments from these private offices with the door closed. Hard copy study records for recruited Birmingham VAMC veterans will be secured in locked file cabinets within locked offices in rooms 8211, 8223, 8224 and 8218 in the BVAMC, with access and key distribution limited to authorized staff. Electronic records will be stored on a VA secure server; only authorized project staff members will have access to the data and the drives/directories on which they are stored. No PHI will be removed from the VA protected environment, nor will any PHI be transmitted electronically. De-identified data sets (data excluding HIPAA identifiers) may be emailed to study statisticians approved by the VA IRB to their UAB email accounts. De-identified data will be stored on secure servers maintained by UAB and accessible solely to study staff on a need-to-know basis. Data sets will be reviewed by the BVAMC Privacy Officer or their representative and will approve all data transfers to UAB. Statisticians will return all analyses to the study PI at BVAMC, and VA data will be deleted from the UAB server when analyses are complete.

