258 participants, age \geq 50 years admitted for any medical illness (e.g. pneumonia, heart failure, COPD exacerbation, or other medical (versus surgical) indication for hospitalization) to either one of the five medical wards of the Birmingham VAMC, or to one of four units at UAB Hospital, will be recruited within 48 hours of hospitalization, and followed throughout their hospitalization and for 12 months after hospital discharge.

Within 48 hours of admission, patients meeting age and ward criteria for the study will be identified daily (as staffing allows) by reviewing the electronic medical record (EMR). Study staff will then contact the medical physician team assigned to the patient and will conduct a brief screening interview with the team to assure the patient meets inclusion and exclusion criteria.

After speaking with the medical team, study staff will meet with eligible patients in their hospital rooms to briefly inform them about the study and ask if they are interested in hearing more details. If a patient expresses interest, the study will be explained and questions answered. Patients will be told they will be visited three times a day and have several assessments done. They will be informed they will be assigned to either MP or UC depending on their ward assignment. All patients will be informed that they will wear a StepWatch®, which counts the steps they take, and that they will be followed with periodic telephone calls for one year after discharge. If the patient is still agreeable, the Mini-Cog^{15,16} and CAM¹⁷ will be administered to aid in determining the patient's decision-making capacity.

If the patient is deemed cognitively intact based on the Mini-Cog and CAM scores, the consent process will continue. If the patient consents, a brief physical screen will be administered: Patients will be asked if they were able to walk across a small room in the 2 weeks prior to admission, and a progressive functional assessment will be administered in which the patient will be asked to sit and then to stand. If the patient successfully completes the physical screening, the patient will be randomized. If a patient is deemed to be unsafe based on the functional assessment within the 36-hour recruitment window, then a referral to physical therapy will be sought from the physician and the patient will not be randomized nor take part in further study activities.

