**Figure 2: StepWatch****Figure 3: StepWatch data output**

(birresearch), accessible only by authorized study staff. No data will be stored in temporary files or on hard drives.

Randomization

Participants will be assigned to MP or UC using cluster randomization based on hospital ward at both the Birmingham VAMC and UAB Hospital. At study initiation, all five wards at the Birmingham VAMC will be assigned to the usual care group. Every 5 months a randomly chosen ward will shift from receipt of usual care to the mobility program (See Figure 4). At UAB Hospital, all four wards will be assigned to the usual care group at study initiation, which is expected to be at month 24 of the study. Every 3 months a randomly chosen study ward will shift from receipt of usual care to the mobility program (See Figure 4A). MP patients will receive three daily visits for progressive ambulation; the UC group will receive three daily “friendly visits.” Both groups will receive routine medical care as it is currently provided, including the provision of physical therapy if ordered by the physician.

Figure 4: Stepped Wedge Cluster Randomization with 5 VA Hospital Units. The order in which each unit receives the intervention is randomized, with staggered implementation. By conclusion of observation, all units have received the intervention. MP (grey bars) = Mobility Program initiated and continued on ward unit.

	Time (in months)						
Unit	1/18/17- 6/18/17	6/19/17 – 11/18/17	11/19/17 – 4/18/18	4/19/18 – 9/18/18	9/19/18 – 2/18/19	2/19/19 – 7/18/19	7/19/19 – 12/31/19
A	Control	MP					
B	Control		MP				
C	Control			MP			
D	Control				MP		
E	Control					MP	

Figure 4A: Stepped Wedge Cluster Randomization with 4 Hospital Units at UAB Hospital. The order in which each unit receives the intervention is randomized, with staggered implementation. By conclusion of observation, all units have received the intervention. MP (grey bars) = Mobility Program initiated and continued on ward unit.

	Time (in months)					
Unit	5/1/18 – 7/31/18	8/1/18 – 10/31/18	11/1/18 – 1/31/19	2/1/29 – 4/30/19	5/1/19 – 7/31/19	8/1/19 – 12/31/19
A	Control	MP				
B	Control		MP			
C	Control			MP		
D	Control				MP	

Daily visits

Mobility Program Group (MP):

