Our primary aim is to evaluate the impact of the mobility program on mobility in the year after hospital discharge using the UAB Life-Space Assessment (LSA). In our previous small VA-funded study of a mobility intervention, patients in the MP group had a mean LSA score that was approximately 10 points higher than in the UC group at four weeks' post-discharge. It is our expectation that the current study will replicate these results; specifically, that the 10-point difference will be apparent at 1-month post-discharge and persist thereafter. As described below, the primary statistical technique to address the primary aim will be mixed effects models. Assuming an exchangeable covariance structure across the repeated observations, a sample size of 190 participants provides greater than 90% power to detect a persistent 10-point difference in LSA scores at the $\alpha = .05$ level. We must also consider the reduced effective sample size due to clustering. It is a common practice to calculate the intraclass correlation (ICC) among clusters as a measure of how much more similar members of the same cluster are to each other than to the overall population. In this setting, we recognize that subjects at UAB may differ from subjects at the VA, leading to differences in the ICC. However, we still expect much more variability to come from individual patient factors than from the units. Using the data from our recently completed VA longitudinal study, we calculated an ICC for the LSA that rounded to 0; including data from UAB resulted in an ICC approximately 4 times larger. Assuming an ICC of 0.004 and subjects spread across 9 units, a sample size of 206 yields an effective sample size of 190 observations. In our recently completed VA longitudinal study during which patients were followed for 6 months after hospital discharge, 80% of the veterans completed at least 5 of the 6 monthly post-hospital assessments. We had 23 deaths and 3 withdrawals over the 6 months of follow-up among the 200 veterans in the study. Thus, in order to have an adequate (i.e. 206) sample size at 12-months, 258 patients will be enrolled allowing for patient losses due to

death or drop outs. Thus, while adding units from UAB to the study does increase the required sample size slightly due to the larger ICC, this is offset by the larger number of potential subjects that can be recruited.

Analytic Approach (for each specific aim)

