- Direct admission to BVAMC or UAB Hospital, or from ED (not from ICU)
- \leq 48 hours since hospital admission
- Access to a telephone after discharge

Exclusion criteria include:

- Inability to walk across a small room 2 weeks prior to admission
- Inability to stand safely with assistance
- Having a diagnosis deemed by the primary physician to be a contraindication to walking (pulmonary embolus, unstable angina, etc.)
- Being on hospice or comfort care
- Non-English speaking, blind, or deaf
- Being enrolled in other VA or UAB mobility research studies
- Isolation precautions for c. difficile, tuberculosis, radioactive treatment, or similar
- Suicidal ideation

Older adults who are either demented or delirious will have the opportunity to participate in this study. Among older adults hospitalized with acute illness, delirium and dementia are common, affecting up to 25% of the population. Exclusion of this group, who may have very different trajectories of recovery after hospitalization, would have a significant impact upon the generalizability of the research results. More importantly, this research may uncover methods by which we can improve hospital care for this vulnerable group who often do poorly when hospitalized.

Screening to determine if a participant has dementia or delirium will occur prior to signed informed consent through use of two standard assessment tools, the Mini Cognitive Assessment (Mini-Cog) and the Confusion Assessment Method (CAM). If a patient scores positively for dementia or delirium based on these tools, the patient's physician will be consulted to determine whether the patient has decision-making capacity. If there is documentation in the EMR or VISTA that the patient does not have decision-making capacity, informed consent will be sought from the appropriate legally authorized representative. Patients with dementia or delirium will be included only if they assent to the study themselves.

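### Patients are recruited after their ward's phase is set, through judgements with no described concealment of that phase, so MP and UC patients may differ at entry, and ward randomization does not protect against this

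*Protocol*

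**What the plan says.** **Allocation.** Protocol section E, Randomization: "Participants will be assigned to MP or UC using cluster randomization based on hospital ward". All wards start in UC. One randomly chosen ward crosses every 5 months at the VA and every 3 months at UAB, and MP then continues on that ward (Figures 4 and 4A). Under Screening, Recruitment & Consent, patients are identified within 48 hours of admission, and the text then says "If the patient successfully completes the physical screening, the patient will be randomized". No patient-level randomization exists: the same section tells patients that their group depends on their ward.

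**Entry decisions.** Three rest on judgement:
- The physician's permission to approach (section C): "if eligible, consent to interview the patient will be requested from the physician".
- The physician's view of the diagnosis (section G, exclusion criteria): "Having a diagnosis deemed by the primary physician to be a contraindication to walking (pulmonary embolus, unstable angina, etc".
- Study staff's view of whether the patient is safe on the sit/stand assessment (section E, Screening, Recruitment & Consent). No scoring rule is given.

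**Blinding.** The SAP's Limitations section deals with the outcome Assessor only.

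**Analysis.** Aim 1 in both documents says that "adjustment for potential confounders will likely be unnecessary as they are expected to be equally distributed between the groups". It goes on to say that confounders such as age, length of stay and CIRS-G will be checked between periods. Any that are dissimilar will be adjusted for, unless deemed a consequence of the intervention.

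**The concern.** Randomizing the order of cross-over protects the comparison of wards. It does not protect against differences among patients chosen after the ward's phase is set. If the people who decide on entry know the phase, the same criterion can be applied differently in the two phases.

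The documents offer a plausible reason for that. MP patients are walked up to three times a day, while UC patients receive social visits. Section J requires two staff to walk with a weak patient or one with a BMI above 35, and the session is skipped if they are not available. That workload recurs throughout an MP stay. In UC it arises mainly at gait-speed tests. Frailer patients could therefore be approached or accepted less often in the MP phase, which would raise MP's post-discharge LSA with no program effect.

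The planned analysis would not remove such a difference by itself. Secular-trend terms describe drift over calendar time, whereas this difference would switch on with the intervention indicator. Intention-to-treat by the unit's assignment at admission cannot undo selection that happened before entry. Neither document plans to compare excluded or refusing patients by phase, so the problem could also go unnoticed.

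**Working it through.** **1. The plan's own figures.** Inputs are from the Protocol, Sample Size Calculations.
- Patients per unit: 206/9 = 22.89. Design effect: 1 + (22.89 - 1) x 0.004 = 1.0876. Effective size: 206/1.0876 = 189.4, against a stated 190. This reproduces.
- Enrolment: 206/0.80 = 257.5, so 258. This reproduces, with the 20% loss inferred from the figures.
- The plan says that "a sample size of 190 participants provides greater than 90% power to detect a persistent 10-point difference in LSA scores", with the expectation that "the 10-point difference will be apparent at 1-month post-discharge and persist thereafter". Neither document gives an SD or a within-patient correlation, so the power cannot be reproduced. If it were exactly 90% at two-sided 0.05, the standard error would be 10/(1.960 + 1.282) = 3.08 points.

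**2. Size of a possible entry shift (assumed inputs).** Let f be the fraction of otherwise eligible patients kept out only in the MP phase, and d the number of LSA points by which they lie below the rest, whose mean is R. The UC mean is R - f x d and the MP mean is R, so the shift is b = f x d. Neither f nor d is in the documents.

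The chance of a significant result under no effect, with the bias in either direction, is 1 - Φ(1.960 - b/3.08) + Φ(-1.960 - b/3.08). Each cell gives the shift in points, then that chance.

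| f | d = 10 | d = 20 | d = 30 |
|---|---|---|---|
| 0% | 0; 0.050 | 0; 0.050 | 0; 0.050 |
| 5% | 0.5; 0.053 | 1.0; 0.062 | 1.5; 0.077 |
| 10% | 1.0; 0.062 | 2.0; 0.099 | 3.0; 0.163 |
| 20% | 2.0; 0.099 | 4.0; 0.254 | 6.0; 0.494 |

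These hold only if post-discharge LSA is compared without baseline adjustment and the entry gap persists in full.

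**3. With baseline LSA used.** A gap that persists in full cancels in a change score. With covariate adjustment at an assumed slope of 0.5 to 0.8, the remaining shift is b x (1 - slope):
- 2 points becomes 1.0 to 0.4.
- 4 points becomes 2.0 to 0.8.
- 6 points becomes 3.0 to 1.2.

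**4. Would the planned balance check catch it?** Figures 4 and 4A give 15 of 35 control ward-periods at the VA and 10 of 24 at UAB, so 25 of 59 overall. Assuming equal recruitment per ward-period, 258 patients split into about 109 UC (258 x 25/59) and 149 MP. Suppose the check were a two-sided 0.05 test on baseline LSA, ignoring clustering. For a 3-point imbalance at SD 20, the standard error is 20 x sqrt(1/109.3 + 1/148.7) = 2.52, 3/2.52 = 1.19, and power is 22%. At SD 25 it is 16% and at SD 30 it is 12%. The SDs are assumed. The plan does not say that the check is a test, nor what counts as similar.

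**The case against.** The strongest reply is that the plan has safeguards. The sentence after the equal-distribution statement commits the team to check confounders and adjust for any that differ. LSA, ADL, IADL and gait speed are scheduled for the first study day, and Aim 1 compares changes in LSA as well as scores. All of that stands, and it is why the table in step 2 is an upper-end illustration. The safeguard is nevertheless incomplete. It acts only if a difference is noticed, it sets no threshold, and it does not name baseline LSA or ADL, which appear only as Aim 2 effect modifiers. It also cannot correct unmeasured differences.

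A reader might infer that physicians will be stricter in the MP phase. The documents do not show this. The written criteria are the same in both phases, and UC patients also stand at screening and walk for gait speed, so a contraindication to walking matters in both.

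A reader might also infer that the people deciding on entry are told the phase. No text says so; what is missing is any step to conceal it.

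Finally, the sentence on randomizing the patient is loose wording rather than a second allocation scheme. Other text already ties assignment to the ward.

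**Conclusion.** The concern holds as a risk built into the design, not as a demonstrated bias. Recruitment follows allocation, entry turns on judgement, no concealment of phase is described, and balance is credited to a randomization that covers ward order only. Following the plan as written could bias the primary test, which is held to this rule: "All statistical tests will be two-sided and will be considered to be significant if the associated p-value is <0.05".

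The direction probably favours MP, if frailer patients are the ones kept out, but this is not certain. The size cannot be taken from the documents. On the assumed ranges (f 0-20%, d 10-30 points) the unadjusted shift is 0 to 6 points against the 10-point target, and less with baseline adjustment or change scores. It would be wrong to read 6 points as an estimate, or to conclude that the plan does nothing about imbalance.

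**What to change.** 1. **Screening (Protocol sections C, E and G).** Put the existing exclusion criterion to the physician in the same words in both phases, without mentioning the phase. Apply the existing sit/stand screen identically. Neither step should change who is eligible.
2. **Baseline.** Complete baseline Part 1 before the participant is told which visits they will receive.
3. **Log.** Record every screened patient with the reason for not entering, by ward and phase. Report these proportions and the baseline characteristics by phase.
4. **Aim 1, both documents.** Replace the equal-distribution assumption with prespecified adjustment for baseline LSA, ADL and CIRS-G, whatever the balance check shows.
5. **Section E, Screening, Recruitment & Consent.** Replace the statement that the patient is randomized with assignment by the ward's phase at admission, in line with the Randomization section and the intention-to-treat rule.

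The cost is a fixed wording, an ordering of steps, a log that existing staff can keep, and a few lines of text. Concealment would be only partial, since ward physicians may recognise the phase. The scheduled ward periods end on 12/31/19 and the protocol is dated February 2021. If accrual has closed, only items 4 and 5 and reporting by phase from retained records remain feasible.
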